10.3. Appendix 3: Assessment Windows

Data will be reported according to the nominal time of clinic visits and assessments as specified in the protocol.

10.4. Appendix 4: Study Phases

Assessments and events collected outside scheduled study visits will be classified into study phases according to the time of occurrence relative to the start and/or stop date of study treatment.

10.4.1. Study Phases for Treatment Period

A treatment period will be considered complete if study treatment was administered. The washout period will start the day after dosing and stop the day before dosing in the next period.

10.4.2. Study Phases for Adverse Event Data

Classification of an AE/SAE as having onset on-treatment will be made with reference to the study treatment dates and the event onset date. If the event onset date is missing, then the event will be considered on-treatment. Events with onset up to 1 day after the date of a treatment will be considered on-treatment.

Study Phase	Definition
Pre-treatment	Events with onset before the first treatment defined as: (onset date < first study treatment dose date or no study treatment dose date)
On-treatment	Events with onset on the day of each treatment and up to 1 day afterwards, defined as: (study treatment dose date <= onset date <= study treatment dose date + 1 or onset date missing)

Events that are not pre- or on-treatment will be presented in listings only

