4. Triplicate ECGs at screening and on Day -1 of each treatment period only. Single ECGs at other timepoints (performed at a similar time of day as Day 1 Pre-dose), unless a reading meets the QTc stopping criteria, in which case two further measurements will be taken at the same time point and the average values captured.
5. Triplicate BP and HR at screening and pre-dose on Day 1 of each treatment period only. Single measurements at other timepoints (performed at a similar time of day as Day 1 Pre-dose). HR and BP assessments only performed at the 24 and 48 hr post dose and early discontinuation/follow-up visit timepoints.

6. Meal (where applicable) to be started and completed 30 minutes prior to danirixin dosing. Meal to consist of 900-1000 calories and be composed of proper caloric content of protein/fat/carbohydrates per FDA guidance and subjects will be required to consume at least 90% of meal.
7. When danirixin dosing occurs in the fasted state, subjects will be provided with a light snack and then will fast from all food and drink (except water) from 10 hours prior to dosing until 4hrs post-dose on Day 1 in each treatment period at which time lunch will be provided. An evening meal will be provided at approximately 9 h post dose. At all other times during residency in the clinic, meals will be provided at appropriate times.

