#### **Part A**

In Part A, approximately 16 healthy elderly participants will be enrolled such that approximately 13 subjects complete dosing and critical assessments for all planned treatment periods. The 16 participants will be randomized and designated to go into one of two (2) groups, Group 1 and Group 2. Group 1 will be administered danirixin in the fed state in all treatment periods. Group 2 will be administered danirixin in the fasted

state in all treatment periods. Participants will undergo a screening period ~30 days prior to the first dose of study treatment, followed by 4 treatment periods with at least a 5 day washout period between each treatment and a follow-up period of 3-10 days following the last dose of danirixin.

Eligible participants will be admitted to the clinical facilities on Day -1 of each treatment period.

On Day 1 of each treatment period, following completion of the required pre-dose measurements and procedures, the investigator or authorized study unit personnel will administer a single oral dose of 50 mg danirixin to each participant in the unit. Following dosing, participants will undergo clinical safety assessments and serial PK assessments at timepoints specified in the Section 2. Participants will be discharged from the unit approximately 24 hours following dosing at the Investigator's discretion.

Participants will return back to the unit on an outpatient basis approximately 48 hours post dose for the 48 hour post dose assessments and be discharged once the assessments are complete at the investigator's discretion. Three to ten days following the last dose of danirixin, participants will return to the clinic for the final follow-up visit. Refer to Section 2 for study assessments and timepoints.

A minimum washout period of 5 days is required between dosing in each treatment period. A study design schematic for Part A is presented in [Table 1](#).

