### **9.2.1. Time Period and Frequency for Collecting AE and SAE Information**

- All SAEs will be collected from the signing of the ICF until the follow-up visit at the time points specified in the SoA ([Section 2](#)).
- All AEs will be collected from the start of treatment until the follow-up visit at the time points specified in the SoA ([Section 2](#)).

- Medical occurrences that begin before the start of study treatment but after obtaining informed consent will be recorded on the Medical History/Current Medical Conditions section of the case report form (CRF) not the AE section.
- All SAEs will be recorded and reported to the sponsor or designee within 24 hours, as indicated in [Appendix 4](#). The investigator will submit any updated SAE data to the sponsor within 24 hours of it being available.
- Investigators are not obligated to actively seek AEs or SAEs in former study participants. However, if the investigator learns of any SAE, including a death, at any time after a participant has been discharged from the study, and he/she considers the event to be reasonably related to the study treatment or study participation, the investigator must promptly notify the sponsor.
- The method of recording, evaluating, and assessing causality of AEs and SAEs and the procedures for completing and transmitting SAE reports are provided in [Appendix 4](#).

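### On-treatment AEs are defined by calendar date, so an AE that starts on a dosing day before the dose is counted against a tablet not yet taken, and Protocol 9.2.1 removes most such events before the first dose only

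*SAP*

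**What the plan says.** SAP 10.4.2 sets the basis: "Classification of an AE/SAE as having onset on-treatment will be made with reference to the study treatment dates and the event onset date". On-treatment means "Events with onset on the day of each treatment and up to 1 day afterwards", given as the formula "study treatment dose date <= onset date <= study treatment dose date + 1 or onset date missing". Pre-treatment means "onset date < first study treatment dose date or no study treatment dose date". For everything else, "Events that are not pre- or on-treatment will be presented in listings only". Neither onset time nor dose time enters the rule.

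SAP section 8 reports safety data by the treatment actually received. By their titles, Tables 3.1 and 3.5 are the on-treatment displays, for AEs and SAEs respectively.

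Protocol 9.2.1 governs what is recorded as an AE. Non-serious AEs are collected once treatment has started, and SAEs from consent. "Medical occurrences that begin before the start of study treatment but after obtaining informed consent will be recorded on the Medical History/Current Medical Conditions" page rather than the AE page.

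There is a pre-dose interval on every dosing day. Participants are admitted on Day -1, and the tablet is given "On Day 1 of each treatment period, following completion of the required pre-dose measurements and procedures" (Protocol 5.1). For fed treatments, Schedule of Activities footnote 6 has the "Meal (where applicable) to be started and completed 30 minutes prior to danirixin dosing". Fasted participants have gone without food overnight, and section 6.3.2 bars caffeine for the preceding 24 hours.

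**The concern.** A headache or nausea that begins on the morning of Day 1, before dosing, cannot have been caused by that day's tablet. Under a date-only rule it is nevertheless tabulated against that tablet. Such events are plausible here: participants have slept in the unit, gone without caffeine, and either fasted or just eaten.

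The second issue is consistency. The recording rule in Protocol 9.2.1 keeps most non-serious events of this kind out of the AE data before the first dose, but not before later doses. If a treatment always falls late in the sequence, its column can collect events that the same circumstances would not add to a treatment given in Period 1. Safety and tolerability is listed among the primary objectives for Part A in SAP 2.2, and the columns are small: about 8 participants per treatment in Part A and 12 in Part B.

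**Working it through.** The plan states no figure on this point, so the check is to apply the rules to example events and then to count periods.

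**Step 1. Apply the SAP 10.4.2 rule.** Doses are taken as 5 days apart (the minimum washout), with dosing at 09:00 as an illustrative assumption. The alternative rule also requires onset at or after the dose time.

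| Onset | SAP rule, Period 1 | SAP rule, later periods | Time-based, Period 1 | Time-based, later periods |
|---|---|---|---|---|
| Day -1 | pre-treatment | listings only | pre-treatment | listings only |
| Day 1, 2 h before dose | **on-treatment** | **on-treatment** | pre-treatment | listings only |
| Day 1, 2 h after dose | on-treatment | on-treatment | on-treatment | on-treatment |
| Day 2 | on-treatment | on-treatment | on-treatment | on-treatment |
| Day 3 (48 h) | listings only | listings only | listings only | listings only |

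Only the pre-dose Day 1 row changes. The SAP rule classes that event as on-treatment in every period, Period 1 included, because pre-treatment requires a date strictly before the first dose date.

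**Step 2. Add the recording rule of Protocol 9.2.1.**

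- Part A and Part B Group 1: a non-serious event before the first dose goes to Medical History and never reaches the SAP rule. The same event before a later dose is an AE and is counted.
- SAEs: collected from consent, so an SAE on Day 1 before the first dose is still counted as on-treatment.
- Part B Group 2: omeprazole starts on Day -4, and Protocol section 7 defines study treatment so as to include marketed products. If omeprazole starts study treatment, 9.2.1 no longer diverts events on Day 1 of Period 1. The documents do not settle this.

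**Step 3. Count the periods in which a non-serious pre-dose event would be counted.** Sequences and planned numbers are from SAP 2.3.

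- Part A: 16 participants / 8 sequences = 2 per sequence. Within each group every formulation comes first in one sequence, so it is in Period 1 for 2 of 8 participants. Counted periods: 8 - 2 = 6 of 8 for every formulation. Balanced.
- Part B Group 1: 12 / 6 = 2 per sequence. E, F and G each come first in two sequences, which is 4 participants; H comes first in none. Counted periods: 12 - 4 = 8 of 12 for each of E, F and G, and 12 - 0 = 12 of 12 for H.
- Part B Group 2 (three periods): I, J and K each come first for 4 of 12. Counted periods: 8 of 12 each if treatment starts with danirixin, or 12 of 12 each if it starts with omeprazole. Balanced within the group either way.

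**Step 4. Scale.** One extra participant with an event is 1/8 = 12.5% of a Part A column or 1/12 = 8.3% of a Part B column. The window spans two calendar days, 48 hours. The documents give no dosing hour. If dosing falls between 07:00 and 11:00, the part before the dose is 7/48 = 14.6% to 11/48 = 22.9% of the clock time. That is a share of hours, many of them overnight, and not a share of events.

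**The case against.** The case for leaving the rule alone has several good points.

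- **Purpose.** The objective is to provide safety information. The planned treatment comparisons are of PK endpoints, and no hypothesis is tested. This stands.
- **Part A.** Each group keeps one meal state throughout and the sequences balance formulations over periods, so formulation columns are affected alike. This stands.
- **Meal effects.** SAP 5.1 makes the meal part of what it calls treatment. Nausea after the assigned meal follows a component already given, so it is not plainly misattributed. This stands for meal-related events, but not for those due to the overnight stay or lack of caffeine.
- **H in Part B.** H is confounded with Period 4 whatever the AE rule, so the rule adds little. True, but H and G share the same high-fat meal, and a counting artefact between them is avoidable.
- **Reach.** By title only Tables 3.1 and 3.5 are restricted to on-treatment events; all AEs are listed, and drug-related AEs have their own table. Largely true, although the listings-only sentence in 10.4.2 leaves open whether other by-treatment tables also depend on the rule.

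A reader might go further and infer that the SAP rule itself exempts Period 1, or that 15% to 23% of on-treatment AEs are misattributed. The documents support neither. The Period 1 exception comes from Protocol 9.2.1 alone and is partial, and the percentage is clock time under an assumed dosing hour.

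**Conclusion.** The point holds and is minor. The date-only rule places any recorded AE with a pre-dose onset on a dosing day in the on-treatment tables under a tablet not yet taken. Periods are not handled alike, because Protocol 9.2.1 diverts most non-serious events of this kind before the first dose only. The one place where this is unbalanced between treatments within a group is Part B Group 1: 12 of 12 planned H periods against 8 of 12 for each of E, F and G. Those are eligible periods, not events.

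This rests on the planned numbers, on equal allocation to sequences, and on sites following 9.2.1 as written. No event rates are given, so the effect on AE counts cannot be estimated. It would not be right to conclude that the Part A formulation comparison is biased.

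**What to change.** In SAP 10.4.2:

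1. Where AE onset time is recorded, require onset at or after the danirixin dose time for on-treatment status, with the upper limit unchanged. Where it is not recorded, keep the date rule.
2. Report pre-dose Day 1 events as a separate category, by period and scheduled treatment. Without this they would drop to listings only in later periods, and meal- or fast-related events would be lost from the tables. Assigning them to the preceding dose would not work: SAP 10.4.1 ends washout the day before the next dose, and with doses at least 5 days apart they would fall outside the preceding window.
3. State whether omeprazole from Day -4 counts as study treatment for AE phasing, in line with Protocol 9.2.1.

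The cost is SAP wording and a small programming change. SAP 5.2 already uses dose time for baseline, and Protocol 7.6 has the time of each clinic dose recorded. The documents do not show that AE onset time is collected, and the SAP describes randomisation and dosing in the past tense, so a new form field may be too late. The downside is that a few events leave the on-treatment count, and nothing is gained where onset time was not collected.

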10.7.2.1. Handling of Missing and Partial Dates

Element	Reporting Detail
General	
 Partial dates will be displayed as captured in participant listing displays.
Adverse Events	
 The eCRF allows for the possibility of partial dates (i.e., only month and year) to be recorded for AE start and end dates; that is, the day of the month may be missing. In such a case, the following conventions will be applied for calculating the time to onset and the duration of the event: 
 Missing Start Day: First of the month will be used unless this is before the start date of study treatment; in this case the study treatment start date will be used and hence the event is considered On-treatment as per Appendix 4: Study Phases. Missing Stop Day: Last day of the month will be used, unless this is after the stop date of study treatment; in this case the study treatment stop date will be used. Completely missing start or end dates will remain missing, with no imputation applied. Consequently, time to onset and duration of such events will be missing.
Concomitant Medications	
 Partial dates for any concomitant medications recorded in the CRF will be imputed using the following convention: 
 If the partial date is a start date, a '01' will be used for the day and 'Jan' will be used for the month If the partial date is a stop date, a '28/29/30/31' will be used for the day (dependent on the month and year) and 'Dec' will be used for the month. The recorded partial date will be displayed in listings.

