10.10.7. Safety Tables

Safety: Tables					
No.	Population	IDSL / Example Shell	Title	Programming Notes	Deliverable [Priority]
Adverse Events (AEs)					
3.1.	mlTT	CP_AE1x	Summary of On-treatment Adverse Events by System Organ Class and Preferred Term	ICH E3	SAC
3.2.	mlTT	CP_AE1x	Summary All Drug-Related Adverse Events by System Organ Class and Preferred Term	ICH E3	SAC
3.3.	mlTT	AE15	Summary of Common (>=5%) Non-serious Adverse Events by System Organ Class and Preferred Term (Number of Subject and Occurrences)	FDAAA, EudraCT Use TD_AE4VCTR macro	SAC
Serious and Other Significant Adverse Events					
3.4.	mlTT	AE16	Summary of Serious Adverse Events by System Organ Class and Preferred Term (Number of Subjects and Occurrences)	FDAAA, EudraCT Use TD_AE4VCTR macro	SAC
3.5.	mlTT	CP_AE1x	Summary of On-treatment Serious Adverse Events by System Organ Class and Preferred Term		SAC

Safety: Tables					
No.	Population	IDSL / Example Shell	Title	Programming Notes	Deliverable [Priority]
3.6.	mlTT	CP_AE1x	Summary of Adverse Events Leading to Permanent Discontinuation of Study Treatment or Withdrawal from Study by System Organ Class and Preferred Term	IDSL	SAC
Laboratory: Chemistry					
3.7.	mlTT	LB1	Summary of Pre-dose Clinical Chemistry Laboratory Values	ICH E3	SAC
Laboratory: Hematology					
3.8.	mlTT	LB1	Summary of Pre-dose Haematology Laboratory Values	ICH E3	SAC
Laboratory: Urinalysis					
3.9.	mlTT	200163 Table 2.17	Summary of Urinalysis Dipstick Data	ICH E3	SAC
Laboratory: Hepatobiliary (Liver)					
3.10.	mlTT	MH2	Listing of Medical Conditions for Subjects with Liver Stopping Events	Only create if there is a liver event	SAC
3.11.	mlTT	SU2	Listing of Substance Use for Subjects with Liver Stopping Events	Only create if there is a liver event	SAC
3.12.	mlTT	LIVER5	Listing of Liver Monitoring/Stopping Event Reporting	Only create if there is a liver event	SAC
3.13.	mlTT	LIVER6	Listing of Liver Stopping Event Information for RUCAM Score	Only create if there is a liver event	SAC
3.14.	mlTT	LIVER7	Listing of Liver Biopsy Details	Only create if there is a liver event	SAC
3.15.	mlTT	LIVER8	Listing of Liver Imaging Details	Only create if there is a liver event	SAC
3.16.	mlTT	LIVER13	Listing of Subjects Meeting Hepatobiliary Laboratory Criteria	Only create if there is a liver event	SAC
ECG					
3.17.	mlTT	CP_EG9	Summary of Change from Baseline in 2h Post-dose ECG Values	IDSL Include all parameters collected	SAC

Safety: Tables					

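### SAP 10.4.2, read literally, leaves every AE or SAE with recorded onset two or more days after a dose out of all summary tables, in conflict with the titles of Tables 3.2, 3.3, 3.4 and 3.6 and with SAP 10.7.1

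*SAP*

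**What the plan says.** SAP 10.4.2 defines two phases for adverse events. Pre-treatment means onset before the first dose. On-treatment is defined as "Events with onset on the day of each treatment and up to 1 day afterwards", and an undated event is also included: "If the event onset date is missing, then the event will be considered on-treatment". Everything else is covered by one sentence: "Events that are not pre- or on-treatment will be presented in listings only". No washout or post-treatment phase is defined for AEs, although SAP 10.4.1 does define a washout: "The washout period will start the day after dosing and stop the day before dosing in the next period".

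The list of safety tables in SAP 10.10.7 uses the on-treatment limit selectively. Table 3.1 is titled "Summary of On-treatment Adverse Events by System Organ Class and Preferred Term", and Table 3.5 is the matching on-treatment table for SAEs. Table 3.2 is titled "Summary All Drug-Related Adverse Events by System Organ Class and Preferred Term". Tables 3.3 (common non-serious AEs), 3.4 (SAEs) and 3.6 (AEs leading to discontinuation or withdrawal) have no phase in the title, and no programming note adds one.

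SAP 10.7.1 says that AE data from withdrawn participants are both listed and put in summary tables. Protocol 9.2.1 collects AEs from the start of treatment, and SAEs from consent, up to the follow-up visit 3 to 10 days after the last dose.

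**The concern.** The listings-only sentence names no table, so on its face it governs all of them. A drug-related AE that starts two days after dosing would then be missing from a table headed as all drug-related AEs. An AE that starts three days after a dose and leads to withdrawal would be missing from Table 3.6, although SAP 10.7.1 says that withdrawn participants' AEs are summarised. Two competent programmers could produce different counts in Tables 3.2, 3.3, 3.4 and 3.6, one following 10.4.2 and the other the table titles.

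Safety and tolerability is a primary objective of Part A and an objective of Part B (SAP 2.2). SAP 8 splits safety displays by treatment received unless stated otherwise. At stake are the completeness of the summary counts and their split by treatment.

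**Working it through.** The plan states no figure to reproduce. The check applies the 10.4.2 definitions day by day to the dosing calendar.

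**Inputs**
- Periods *p*: 4 in Part A and Part B Group 1, 3 in Part B Group 2 (SAP 2.3).
- Dose spacing *s*: 5 days if the minimum washout runs from dose to dose (Schedule of Activities footnote 2), or 6 if five full days must lie between doses as SAP 10.4.1 draws the washout. Both are minimum spacings.
- Follow-up *f*: 3 to 10 days after the last dose.
- On-treatment window: 2 days per dose.

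**Formulas**, counting from the first danirixin dose to follow-up inclusive:
- Collection days N = (p − 1)s + f + 1
- Days outside the window = N − 2p

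**Results if only danirixin dates count as dose dates**

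| Group | s | f = 3 | f = 10 |
|---|---|---|---|
| Four periods | 5 | 11/19 = 57.9% | 18/26 = 69.2% |
| Four periods | 6 | 14/22 = 63.6% | 21/29 = 72.4% |
| Part B Group 2 | 5 | 8/14 = 57.1% | 15/21 = 71.4% |
| Part B Group 2 | 6 | 10/16 = 62.5% | 17/23 = 73.9% |

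Longer spacing raises the share. At 7 days it is 68-75% with four periods and 67-76% with three.

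**Results in Part B Group 2 if omeprazole dates also count.** Omeprazole is taken daily to the Period 3 48-hour assessment, which is last danirixin dose + 2. The window then runs unbroken to last dose + 3, and the days outside are f − 3. That gives 0/14 to 7/21 (0-33.3%) at s = 5 and 0/16 to 7/23 (0-30.4%) at s = 6. Part A and Part B Group 1 do not change.

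**What the literal rule does to each table**
- Table 3.2: non-serious AEs are collected only from the start of treatment, so the table would in effect hold on-treatment events only, despite its title.
- Table 3.3: the same holds, although the title gives no limit.
- Table 3.4: it could exceed Table 3.5 only by pre-treatment SAEs.
- Table 3.6: an AE that starts at dose date + 2 or later and ends participation is left out, contrary to SAP 10.7.1.

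**The case against.** The strongest reply is that the sentence was never meant to reach beyond Tables 3.1 and 3.5. Only those two titles say on-treatment. SAP 8 says that all collected data are reported, and SAP 10.7.1 summarises withdrawn participants' AEs. The introduction to SAP 10.4 speaks of events collected outside scheduled visits, so it is less certain that events collected at visits are all caught. This may well be the intention, but the sentence does not say so and the conflict remains on the page.

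Several stronger inferences are tempting, and the documents do not support them.
- *Events are lost from the report.* They are not. Listings 15-21 keep them all.
- *Most adverse events are left out.* The shares are of days. The documents give no AE rates, and classification goes by onset date, so an event reported at the 48-hour visit with onset on the dose date or the next day stays on-treatment.
- *Planning Table 3.4 beside Table 3.5 proves the contradiction.* SAEs are collected from consent, so 3.4 can properly exceed 3.5 by pre-treatment SAEs, and the two use different display shells. The pairing only suggests that 3.4 was meant to be unrestricted.
- *The sponsor has no rule for assigning later events to a treatment.* The SAP text gives none, but the reporting standards and mock shells it relies on are not in the documents.
- *The one-day window or the missing-onset rule is wrong.* A short pre-specified window is a legitimate choice in a descriptive single-dose study. Counting undated events as on-treatment is compatible with SAP 10.7.2.1, which leaves wholly missing dates unimputed.

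**Conclusion.** The point holds as a conflict within the SAP. A stated rule, followed as written, gives incomplete counts in Tables 3.2, 3.3, 3.4 and 3.6 and contradicts SAP 10.7.1 for withdrawn participants. It covers more than half of AE-collection days in the four-period groups (58-72%). In Part B Group 2 it covers 57-74% if dose dates are danirixin dates, as SAP 5.1 and 10.4.1 suggest. The Group 2 share falls to about 0-33% if omeprazole dates count, a reading left open because Protocol 7 includes marketed products in study treatment and its treatment table lists omeprazole. The ranges assume minimum dose spacing and follow-up at 3 to 10 days.

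The consequence is confined to summary counts and their split by treatment, since the listings are complete. It is worth correcting before the tables are programmed.

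**What to change.** 1. In SAP 10.4.2, limit the listings-only sentence to Tables 3.1 and 3.5.
2. State that Tables 3.2, 3.3, 3.4 and 3.6 include all post-dose events up to follow-up. Assign each event to the treatment last received, from the dose date to the day before the next dose (the boundary already in SAP 10.4.1) and, after the last dose, to follow-up. Say in the same place whether dose date means danirixin dose date.
3. Show pre-treatment SAEs in Table 3.4, in a separate pre-treatment column or in the Part/Group total.
4. Leave the missing-onset rule, and the dose date + 1 window for Tables 3.1 and 3.5, as they are. An extra table of all post-dose AEs by treatment is optional.

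If the sponsor did intend the restriction for every table, the titles of 3.2, 3.3, 3.4 and 3.6 and the statement in SAP 10.7.1 must be changed to say so. The documents do not show which was meant.

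The cost is a few lines of SAP text, a date condition in the code and one column or total in Table 3.4, with no new data. The downside is that some unrelated late-washout events will be attributed to the preceding treatment. If the optional table is produced, comparing it with Table 3.1 shows how many events fall after the dose date + 1 window.
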